#### **Phone Visit 3 (midway between Week 8-12)**

During the time interval between visits, the site coordinator contact (via telephone) the subjects.

1. Review subject's eDiary. If there is any missing entry, re-instruct the subject to record the eDiary daily.
2. Ensure to record the eDiary correctly.
  - a. Perform and record scoring of the pain of the target knee using the NRS 11-point pain scale when subjects replace a patch. In addition to the regular assessment of NRS, the NRS assessment will be performed immediately before the subject takes any rescue medication on the day (if applicable).
  - b. Record the time of patch application and removal when subjects replace a patch.
  - c. Record the time of not scheduled complete patch detachment and the reason (if applicable) at the time of unscheduled detachment or before they sleep.
  - d. Record the number of tablets of rescue medication used, the time and the reason when subjects take a tablet or before they sleep.

- e. Answer the questionnaires related to adhesion, skin irritation and discomfort when subjects replace a patch and record any issues with adhesion, skin irritation and discomfort.
3. Re-instruct the subject concerning the patch application and removal method.
4. Review AEs. The irritation and discomfort reported in the eDiary will be treated as AEs.
5. Review subject's use of concomitant medication.
6. The subjects will be informed by the site personnel that they may contact the site if problems/questions arise.
7. **Patient Education:** At all clinical study visits, the investigator (or designee) will explain the importance of the following:
  - a. applying study drug [REDACTED] [REDACTED] to the target knee (where required, showering/bathing should be done prior to patch application);
  - b. keep the patch attached [REDACTED] including while sleeping;
  - c. recording patient eDiary information [REDACTED] when subjects replace the patch, take the rescue medication and before they sleep;
  - d. accurately reporting pain;
  - e. accurately reporting rescue medication use;
  - f. understanding when to return for their next visit and the importance of returning on schedule;
  - g. adhering to the overall research plan; and
  - h. Do NOT apply study drug to non-target knee at any time.

### **Visit 8 (Week 12)**

1. Perform physical examination.
2. Obtain vital signs measurements.
3. Obtain subject's weight.
4. Obtain blood and urine samples for laboratory testing.
5. Perform a 12-lead ECG.
6. Perform a pregnancy test.
7. Administer the WOMAC questionnaire for the target knee.
8. Perform PGA.
9. Perform PGIC.
10. Perform a QOL Questionnaire.
11. Perform dermal safety assessment (irritation, discomfort, and adhesion) and record the time of the evaluation for each assessment in the eCOA.

12. Remove the patch on a skin.
13. Instruct a subject to perform the following assessments in the eDiary when they remove the patch at the site:
  - a. Perform and record scoring of the pain of the target knee using the NRS 11-point pain scale
  - b. Record the time of patch removal.
  - c. Record the time of not scheduled complete patch detachment and the reason (if applicable).
  - d. Record the number of tablets of rescue medication used, the time and the reason.
  - e. Answer the questionnaires related to adhesion, skin irritation and discomfort.

Record any issues with adhesion, skin irritation and discomfort.
14. Review the subjects' eDiary entries.
15. Collection of unused study drug and rescue medication.
16. Review subject's use of rescue medication/concomitant medication.
17. Perform drug accountability/reconciliation of study drug and rescue medication. The reconciliation (missing patch, failure of application, unscheduled detachment and application, etc.) will be recorded in the eCRF.
18. Review AEs. The irritation and discomfort reported in the eDiary will be treated as AEs.

**Note: After Visit 8, subjects may resume their standard of care treatment.**

#### **10.1.4 Follow-up Phase**

A follow-up phone Visit will take place approximately 7 days after Visit 8 (or Early Termination Visit), and will include the following assessment and procedures:

1. Review subject's use of concomitant medications.
2. Review AEs.
3. Record the findings in the eCRF.

#### **10.1.5 Early Termination Visit (if applicable)**

Subjects who are discontinued prematurely from study for any reason after Baseline (Visit 3) must complete the Early Termination Visit. If the subject comes for an Unscheduled Visit and a decision to withdraw the subject is made, then the Early Termination Visit procedures will be performed and the Early Termination Visit eCRF will be completed (and not the Unscheduled Visit eCRF).

During this visit the following assessments and procedures will be performed:

1. Perform physical examination.
2. Obtain vital signs measurements.

3. Obtain subject's weight.
4. Obtain blood and urine samples for laboratory testing.
5. Perform a urine pregnancy test.
6. Perform a 12-lead ECG.
7. Administer the WOMAC questionnaire for the target knee.
8. Perform PGA.
9. Perform PGIC.
10. Perform a QOL Questionnaire.
11. Remove the patch on a skin.
12. Instruct a subject to perform the following assessments in the eDiary when they remove the patch at the site:
  - a. Perform and record scoring of the pain of the target knee using the NRS 11-point pain scale
  - b. Record the time of patch removal.
  - c. Record the time of not scheduled complete patch detachment and the reason (if applicable).
  - d. Record the number of tablets of rescue medication used, the time and the reason.
13. Review the subjects' eDiary entries.
14. Collection of unused study drug and rescue medication.
15. Review subject's use of rescue and concomitant medications.
16. Perform drug accountability/reconciliation of study drug and rescue medication. The reconciliation (missing patch, failure of application, unscheduled detachment and application, etc.) will be recorded in the eCRF.
17. Perform dermal safety assessment (irritation, discomfort, and adhesion).
18. Review AEs. The irritation and discomfort reported in the eDiary will be treated as AEs.
19. Record the date and the reason of early termination in the eCRF.

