### 10.1.2 Baseline Visit (Visit 3, Day 0)

The subject must be screened and the Washout Visit performed prior to the Baseline Visit. The following will take place during the Baseline Visit (Visit 3, Day 0):

1. Confirm subject's continued eligibility relative to inclusion/exclusion criteria.
2. Review subject's use of prior/concomitant medications.
3. Obtain vital signs measurements.
4. Perform an NRS 11-point pain assessment **for the non-target knee pain.**
5. Administer the WOMAC questionnaire for the target knee.
6. Perform Patient Global Assessment (PGA).
7. Review the subjects' eDiary entries. If there is any missing entry, re-instruct the subject to record the eDiary daily.
8. eDiary NRS 11-point pain scores will be reviewed by the investigator or the study coordinator. [REDACTED]

will be entered to the eCOA system and the mean NRS scores will be calculated. If the score of the 1 day before of Baseline Visit is missing, the subject will be excluded from the study.

9. Perform a 12-lead ECG.
10. Obtain blood and urine samples for laboratory testing.
11. Perform a drug (urine), alcohol (breathalyzer) and pregnancy (urine) tests.
12. Perform Baseline dermal safety assessment (irritation only).
13. Record the eligibility of the subject in IWRS. If the subject screen fail, the date and the reason will be recorded in IWRS.
14. Randomly assign the subject to a treatment group using IWRS.
15. Perform a QOL Questionnaire.
16. Placebo training will be performed to educate subjects. The aim is to minimize the placebo response and increase their awareness for the purpose of the trial to determine a new drug is effective and safe.
17. Collection of unused rescue medication. Note: Do not dispense rescue medication. Rescue medication is prohibited from Visit 3 until Visit 4.
18. Perform rescue medication accountability/reconciliation.
19. Instruct the subject concerning the patch application and removal method including how to rotate the patches **by using** a video and a separate manual/guide.
20. Dispense the double-blind study drug and instruct subjects on proper patch application. The first patch will be applied on the target knee at sites. Subjects will be instructed to

replace the patch [REDACTED]

[REDACTED] after showering/bathing. [REDACTED]

[REDACTED] Subjects will be instructed not to bathe or shower while wearing the study drug.

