#### **10.3.2.4.1 Patch Adhesion**

Patch adhesion will be assessed in 2 ways: in-clinic and at-home. At each clinic visit, patch adhesion will be assessed by the investigator or a designee (who will be a trained medical professional such as a nurse practitioner or physician assistant) using the following 5-point numerical scale:

- 0 =  $\geq 90\%$  adhered (essentially no lift off the skin).
- 1 =  $\geq 75\%$  to  $< 90\%$  adhered (some edges only lifting off of the skin).
- 2 =  $\geq 50\%$  to  $< 75\%$  adhered (less than half of the system lifting off of the skin).
- 3 =  $< 50\%$  adhered but not detached (more than half the system lifting off of the skin without falling off).
- 4 = patch detached (patch completely off the skin).

During the Double-blind Treatment Phase at home, subjects will report on any incidence of unscheduled patch detachment, the time and the reason and record in the eDiary. When subjects replace the patch, subjects will complete a questionnaire about adhesion and residue in the eDiary to confirm the following:

- Is the patch 100% attached to the skin? If No, is more than half of the patch still attached?
- Is there any residue on your skin after removing the patch?

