18.7 OTHER SAFETY ASSESSMENTS

18.7.1 DERMAL EVALUATIONS AT CLINIC

18.7.1.1 Patch Adhesion

Results of patch adhesion assessed at clinic and collected in the *Dermal Evaluations* eCRF form will be tabulated by visit and overall, for each treatment group. The frequency and percentage of patches in each category will be summarized, per the 5-point numerical scale described below, for each visit and overall. Also, for each patch adhesion score category, the number and percent of subjects with worst score in the specific category is presented by treatment group.

The following 5-point numerical scale is used to assess the patch adhesion:

Noven Pharmaceuticals, Inc.

Protocol HP-5000-US-07

Statistical Analysis Plan

Page 45 of 58

0 = ≥90% adhered (essentially no lift off the skin).
1 = ≥75% to <90% adhered (some edges only lifting off of the skin).
2 = ≥50% to <75% adhered (less than half of the system lifting off of the skin).
3 = <50% adhered but not detached (more than half the system lifting off of the skin without falling off).
4 = patch detached (patch completely off the skin).

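### The Early Termination list puts patch removal before the dermal assessment, so an adhesion score of 4 there may reflect planned removal rather than detachment

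*Protocol*

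**What the plan says.** Protocol 10.1.5 numbers the ET procedures. Step 11 is "11. Remove the patch on a skin". Step 12 is the eDiary entry at removal: pain score, removal time (12b), any unscheduled complete detachment with its reason (12c), and rescue use (12d). The dermal assessment follows at step 17: "17. Perform dermal safety assessment (irritation, discomfort, and adhesion".

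The Visit 8 (Week 12) list in Protocol 10.1.3 runs the other way. Step 11 is "11. Perform dermal safety assessment (irritation, discomfort, and adhesion) and record the time of the evaluation for each assessment in the eCOA", and step 12 is "12. Remove the patch on a skin". Its eDiary entry also has an item 13e, the subject's questionnaire on adhesion, irritation and discomfort. ET step 12 has no counterpart.

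On the adhesion scale (Protocol 10.3.2.4.1) the top score is "4 = patch detached (patch completely off the skin". The discomfort scale (10.3.2.4.3) has its own code 4 for an absent patch. For the analysis, SAP 18.7.1.1 says that "for each patch adhesion score category, the number and percent of subjects with worst score in the specific category is presented by treatment group". SAP 6.3 brings early discontinuation visits into the by-visit analyses by windowing.

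**The concern.** Adhesion describes a patch that is being worn. A site that follows the ET list in order would score adhesion on a knee from which its own staff have just taken the patch. The scale has no entry for that situation other than 4, the same score that a true detachment gets. A blank field is the alternative.

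Adhesion and discomfort are stated safety endpoints (Protocol 13.1.4, SAP 2.3). For a patch product, subjects who leave early are of particular interest, because some may leave over adhesion or skin problems. Their last reading would be either an artificial worst score or missing. If the two arms had different numbers of ET visits, the artefact would also differ by arm.

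**Working it through.** No figure in the plan is at issue, so the check sets the passages side by side.

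| Item | Visit 8 | ET visit |
|---|---|---|
| Dermal assessment | step 11 | step 17 |
| Patch removal | step 12 | step 11 |
| Time of each evaluation requested | yes | no |
| eDiary removal time | 13b | 12b |
| eDiary unscheduled detachment | 13c | 12c |
| eDiary dermal questionnaire | 13e | none |

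Both protocol versions in the file have the same ET order, so the amendment did not change it.

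**Adhesion.** The scale grades the share of the patch still adhered. With the patch off, scores 0 to 3 cannot apply and 4 is what remains. The scale has no category for removal by staff.

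**Discomfort.** The evaluator asks about patch-related discomfort and rates it none, mild, moderate or severe. That question can still be answered just after removal. But code 4 is also available and literally true at that moment, so two sites could code the same subject differently. SAP 18.7.1.2 names the four ratings from none to severe as the reported categories, yet keeps 4 on the scale and tabulates each subject's worst score. If worst is taken as the numerical maximum, 4 outranks a genuine 3.

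**Irritation.** Protocol 10.3.2.4.2 reads it where the previous patch was applied, and SAP 18.7.1.3 describes it as done after removal. The ET order does no harm here.

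**Route to the tables.** The worst-score table takes a 4 at face value. By-visit tables can receive the ET reading through the SAP 6.3 windows, unless another assessment in the same window lies closer to the target day. Neither section has a rule for a score taken after planned removal.

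**Can it be sorted out later?** Visits 4 to 8 all ask for the time of each dermal evaluation. ET step 17 does not. Removal time is recorded (12b), but without an evaluation time to set against it, the order cannot be established from these fields.

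**Size.** The points added to the worst-score-4 category in an arm are

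added share = p × q × r,

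where p is the share of the arm with an ET visit while wearing a patch, q the share of those coded 4 after removal, and r the share of those with no earlier 4. The documents give none of these. As an illustration only, assume p = 10% to 20%:

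- q = r = 1: 10 to 20 percentage points, the ceiling under that assumption.
- q = 0 (sites score before removing, or leave the field blank): 0 points.

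**The case against.** The strongest reply is that the numbered list is not a required sequence. Its lead-in says only "During this visit the following assessments and procedures will be performed". The protocol's visit lists are visibly not chronological. The Baseline list opens with "1. Confirm subject's continued eligibility relative to inclusion/exclusion criteria", although the Baseline WOMAC pain score, an inclusion criterion, is collected at step 5. Adhesion is scored by the investigator or a trained medical professional, who may well look at the patch before taking it off. This stands. A reader might infer that ET subjects cannot be given a valid adhesion score, and the documents do not support that. They support only that the score may be taken after removal if the listed order is followed. The reply does not dispose of the point, because a mixture of sites doing it either way could not be detected without evaluation times.

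A reader might also infer that removal and detachment become indistinguishable. That goes too far. ET items 12b and 12c record removal and unscheduled detachment separately, and SAP Appendix 4 refers to an eCRF page for patch removal at the final visit. The worst-score table as specified uses none of these, but the data could help.

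The gap in subject-reported data is narrow. The questionnaire is completed at every patch replacement (Protocol 10.1.3, home procedures), so only the last patch at ET lacks an explicit instruction. Finally, some ET subjects may already have stopped patches while staying in the study (Protocol 8.2.3). No adhesion score is possible for them in either order.

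**Conclusion.** The reversal is confirmed and should be corrected. Followed as listed, the ET procedure can give an adhesion score of 4 that reflects only removal by staff, and an ambiguous discomfort code. The ET list does not collect the time needed to recognise this.

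The reach is limited. It concerns ET subjects who arrive wearing a patch, and only descriptive dermal summaries, for which no formal inference is planned unless otherwise noted (Protocol 13.4.4, SAP 18). The primary endpoint, the type I error rate and the sample size are untouched.

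The size is unknown. A reader might take the 10 to 20 points above as an estimate. It is a ceiling that rests on an assumed ET share, on every such subject being coded 4 after removal, and on none having scored 4 before. The true effect could be zero. A difference between arms is likewise conditional on unequal ET rates or unequal site practice, neither of which the documents establish.

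**What to change.** In Protocol 10.1.5:

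- Move the adhesion and discomfort assessment ahead of patch removal, as at Visit 8. Irritation need not move.
- Add the instruction to record the time of each evaluation.
- Add Visit 8's item 13e questionnaire to step 12.

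In SAP 18.7.1, state that an adhesion or discomfort code of 4 due only to planned removal at the site is treated as not assessed and is not counted as the worst score.

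For ET readings already taken, check source records and the eDiary removal and detachment times (12b and 12c) before any recoding. A blanket change of every ET score of 4 to not assessed would erase true detachments.

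The cost is one reordered list, one existing questionnaire item, one time entry already requested at Visits 4 to 8, and one sentence in the SAP. No new visit or assessor is needed. The source check is the only real work, and it is confined to ET subjects with a code of 4.

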## 10.2. The Schedule of Events

Phase	Screening Phase			Double-blind Treatment Phase									Follow-up	ET
	Screening k	Washout k	Baseline	1	2	4	8	12	13					
Week			0											
Clinic visit	1	2	3	4	5	6	7	8	12					
Phone Visit a					1		2	3					4	
Day	-28 to -10	-14 to -7	0	1-6	7	8-13	14	15-27	28	29-55	56	57-83	84	91
Visit Window (Days)				±2	±2	21±3	±2	42±3	±7	70±3	±7		±2	
Informed Consent	X													
Demographics	X													
Medical History	X													
Inclusion/Exclusion criteria	X	X	X											
Randomization			X											
Physical Examination	X										X		X	
Vital signs	X		X		X	X	X	X	X	X	X	X	X	
Height	X													
Weight	X										X		X	
Clinical Laboratory test b	X		X				X				X		X	
Urine Pregnancy Test	X		X					X	X	X	X	X	X	
Drug Screen/ Alcohol Test	X		X											
12-lead ECG	X		X								X		X	
X-Ray c	X													
Dispense Rescue Medication		X			X	X	X	X	X					
Use of Rescue Medication d	X	X			X	X	X	X	X	X	X	X		X
Study Drug Application e			X	X	X	X	X	X	X	X	X	X	X	
Collection of Unused Study Drug and Rescue Medication			X f		X	X	X	X	X	X	X	X	X	X
Drug Accountability			X f		X	X	X	X	X	X	X	X	X	X
Patient eDiary f	X	X	X	X	X	X	X	X	X	X	X	X	X	X
Pain Intensity 11-Point NRS	X	X	X	X	X	X	X	X	X	X	X	X	X	X
Dermal Evaluations g			X		X	X	X	X	X	X	X	X	X	X
WOMAC h	X		X		X	X	X	X	X	X	X	X	X	X
PGA			X		X	X	X	X	X	X	X	X	X	X
PGIC					X	X	X	X	X	X	X	X	X	X
QOL Questionnaire i			X					X			X		X	X
Placebo training		X	X											
Prior/Concomitant medications	X	X	X	X	X	X	X	X	X	X	X	X	X	X
Adverse Events j			X	X	X	X	X	X	X	X	X	X	X	X

Abbreviations: AE = adverse event; eDiary = electronic diary; ET = early termination; ECG = electrocardiogram; NRS = numeric rating scale; PGA= Patient Global Assessment; PGIC=Patient Global Impression of Change; WOMAC = Western Ontario and McMaster Universities Arthritis Index; QOL = quality of life.

- a Principal Investigator or designee contacts subjects approximately midway between Weeks 2-4 (Day21±3), 4-8 (Day42±3), and 8-12 (Day70±3).
- b Clinical laboratory testing includes hematology, biochemistry, urinalysis, and fasting glucose and lipids. Fasting glucose and lipids should be performed after 8 to 10 hours of fasting (no food or drink, except for water). Fasting is necessary for all laboratory tests. However, if the subject is not able to fast at Visit 1, at least fasting at Visit 3 should be done during Screening Phase.
- c Historical X-rays done within 1 year prior to the Baseline Visit are acceptable. If subject does NOT have any target knee X-ray done within the past year, a mandatory new X-ray to confirm the disease will have to be performed prior to starting the Washout Period and the X-ray should be reviewed by the completion of Baseline Visit.
- d If needed, subjects will be allowed to take up to a maximum of 2 g (4 × 500 mg tablets) of oral acetaminophen per day as rescue medication for the treatment of the target knee pain of OA because of lack of efficacy of study drug (not for the non-target knee) if the subject does not feel enough pain relief by the study drug, any other aches they might experience during the trial such as headache and reduction of fever except within 3 calendar days prior to the Baseline Visit, on the day of Baseline Visit (V3), from Baseline Visit until Visit 4, within 2 calendar days prior to for all subsequent visits (V5, V6, V7, and V8), and on the day of the clinic visits (V4, V5, V6, V7, and V8).
- e Study treatment will be applied on Day 0 at sites. Instructions for application and removal of study drug patches will be provided to the subject at Baseline visit.
- f Subjects will be instructed on how to use the eDiary at the Screening Visit. For Screening Phase, subjects will be asked to record their NRS pain scores of the target knee and the number of tablets of rescue medication used, the time and the reason in the eDiary. For 12-week administration period, subjects will be asked to record their NRS pain scores of the target knee, and the number of tablets of rescue medication used, the time and the reason, unscheduled detachment of study drug and the reason and answer the questionnaire related to adhesion, skin irritation and discomfort, record any issues with adhesion, skin irritation and discomfort in the eDiary.
- g Dermal evaluations will assess irritation, discomfort, and adhesion (At Visit 3, irritation only).
- h WOMAC will include WOMAC pain intensity, WOMAC stiffness, and WOMAC physical function.
- i QOL Questionnaire is Mini-OA Knee and Hip QOL (Mini-OAKHQOL) and Work Productivity and Activity Impairment Questionnaire for Osteoarthritis (WPAI: OA).
- j AEs will be collected starting from the first administered dose.
- k Screening visit (Visit 1) will be completed -28 to -10 days prior to Baseline Visit. Washout visit (Visit 2) is at least 3 days after Visit 1 (e.g. If Visit 1 is Day -10, Visit 2 can be scheduled on Day -7). Washout visit (Visit 2) will be completed -14 to -7 days prior to Baseline Visit. Washout Period will be initiated from the Washout Visit (Visit 2). Washout period is for 7 to 14 days.
- l Only for rescue medication.

